6.2.3.1 Feedback about the SPT

HCPs will complete a survey providing their feedback about the SPT using a VAS.

6.2.3.2. Assessment of experience with SPT

Participants will complete a survey regarding their overall experience with the SPT using a VAS.

6.3. End of participant activity

The HCPs will remove the SPT from the target areas of the participants after all study activities have been completed. Thereafter, the participants will be dismissed from the study.

If the skin fold conditions in the target area(s) of any participant resolve before Day 5, the last day of study participation will occur on that day (earlier than Day 5). All activities planned for Day 5 should be carried out on the last day of study participation in order for participants to have complete data.

Note: Should the PI or qualified designee determine that continued treatment of the skin fold condition(s) beyond five days is necessary, such treatment must be administered per hospital procedures and using materials from hospital inventory. Study materials must be reserved for up to six days of participant enrollment.

6.4 Scoring of erythema, maceration, denudation, and satellite lesions in the target areas

After the participants have been dismissed from the study, a third-party clinician will score the skin fold conditions such as erythema, maceration, denudation, and satellite lesions in the participants' target area(s) using photographs taken by the PI or qualified designee and Likert scale(s) developed for the study.

For each participant, the photographs for each type of skin fold condition for Days 0, 1, 3, and 5 (or the last day of study participation [ie, fully healed target area(s)]) will be bundled and provided (in the order in which the photographs are taken) to the third-party clinician.

7. ADVERSE DEVICE EVENTS (ADEs)

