This study will evaluate the efficacy of the SPT to manage erythema, maceration, denudation, satellite lesions, pain, itching, burning, moisture, and odor associated with skin folds (henceforth together referred to as “skin fold conditions”). Participants will be patients with skin fold conditions, which will be treated with the SPT. Healthcare providers (HCPs) will apply the SPT to the participants’ skin folds and other skin-on-skin contact areas (henceforth referred to as “target area[s]”). An independent licensed clinician with experience in identifying and treating skin fold conditions (henceforth referred to as “third-party clinician”), will use photographs of the target areas to assess the status of erythema, maceration, denudation, and satellite lesions in the target areas when the SPT is first applied (Day 0), and on Days 1, 3, and 5 (or the last day of study participation [ie, fully healed target area(s)]), during SPT changes. The PI or qualified designee will take photographs of the target areas and assess moisture and odor in these areas. Participants will provide their impressions of pain, itching, and burning in the target area(s) on the same days as the skin fold condition photography. In addition, the study will include feedback from the HCPs about the SPT and overall experience of the participants with the SPT.

Phase:	Post-market
Primary Objective:	To evaluate the efficacy of the SPT to improve skin fold conditions.
Secondary Objectives:	
1. To gather PI or qualified designee's assessment of moisture control in the target areas.2. To assess HCP feedback on the SPT.3. To assess the overall participant experience with the SPT.

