Primary Endpoint:	
1. Improvement in skin fold conditions such as erythema, maceration, denudation, satellite lesions, odor, pain, itching, and burning over five days of treatment.
1a. Likert scales developed for erythema, maceration, denudation, and satellite lesions. Scoring of the target area(s) done by a third-party clinician using the Likert scale(s) and photographs taken by the PI or qualified designee on Day 0, and on Days 1, 3, and 5, during SPT changes.1b. Assessment of odor in the target area(s) on Day 0, and on Days 1, 3, and 5, during SPT changes, using a Likert scale.1c. Participant assessment of discomfort (pain, itching, and burning) using a visual analogue scale (VAS) on Day 0, and on Days 1, 3, and 5, during SPT changes. Participants will also be asked to identify the most prominent type of discomfort in the skin fold: pain, itching, or burning.
Secondary Endpoints:	
1. PI or qualified designee survey responses for moisture in the target area(s) on Day 0, and on Days 1, 3, and 5, during SPT changes, using a Likert scale.2. HCP survey responses on Day 5, regarding their feedback about the SPT, using a VAS.3. Participant responses on Day 5, regarding their experience with the SPT, using a VAS.
Note:	All endpoint-related activities planned for Day 5 will be carried out for the last day of study participation (ie, fully healed target area[s]) if it occurs before Day 5.
Study Population:	Number of target areas, N = 119. Participants can be the source of up to two target areas, and each target area can have more than one skin fold condition. Per the assessment of the PI or qualified designee, the skin fold conditions of the participants must be anatomically distant enough to allow the participants to make an objective assessment of discomfort (pain, itching, and burning) in each target area. A participant may be re-enrolled using a new participant study identification (ID) number for another set of up to two target areas at a different location. The target areas must be anatomically distant (per the assessment of the PI or qualified designee), as described above.

Inclusion criteria

Individuals who meet all of the following criteria will participate in this study:

- Individuals \geq 18 years of age.

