4. STUDY DESIGN

4.1. Overall Design

This is a prospective unblinded study in which the effectiveness of the SPT in the management of participants with skin fold conditions such as erythema, maceration, denudation, satellite lesions, pain, itching, burning, moisture, and odor will be evaluated. As part of the screening process, the PI or qualified designee will examine and document the skin fold conditions to identify potential target area(s) prior to application of the SPT to these areas (Day 0). The PI or qualified designee will take photographs of the target areas using a wound camera system once the participants are enrolled in the study (Day 0). The HCPs will apply the SPT to the target area(s) of the participants as described in the Instructions for Use (IFU). The PI or qualified designee will again take photographs of the target areas using the wound camera system on Days 1, 3, and 5 (or the last day of study participation [ie, fully healed target area(s)]), during SPT changes. On days when the target areas are photographed, the PI or qualified designee will also assess moisture and odor using Likert scales, and participants will provide their impressions of pain, itching, and burning in the target area(s) using a VAS survey. Participants will also be asked to identify the most prominent type of discomfort during this assessment. On Day 5 or the last day of study participation (ie, fully healed target area[s]), as applicable, VAS surveys will be used for the following: (1) HCP feedback about the SPT, and (2) Overall participant experience with the SPT. After the participants are dismissed from the study, a third-party clinician will score the status of erythema, maceration, denudation, and satellite lesions in the target areas using the photographs taken by the PI or qualified designee and the Likert scales developed for the study.

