8.2. Randomization

No randomization is planned at this time.

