8.5. Interim Analysis

Two interim analyses will be performed at 34% and 67% completion, testing for early efficacy or futility, using t-score boundaries that follow O’Brien-Fleming Analog alpha and beta spending rules. Assuming that the two interim analyses will occur after approximately 40 (1/3 of 119 total target areas) and 80 (2/3) target

areas have been assessed and adjudicated, the nominal alpha levels to reject the null hypotheses for efficacy are as follows in the table below.

Analysis Order	Number of Target Areas	Nominal critical point (Z-value)	Alpha level
1	40	-4.42	0.00000
2	80	-3.09	0.00122
Final	119	- 2.406	0.00804

Futility analyses are planned to be conducted to coincide in timing with the tentative interim analyses. The formal criterion for determination of futility is that at each interim look, if the condition power (defined as the probability of rejecting the null hypothesis at the final analysis given the data accumulated so far and under the assumption that the alternative hypothesis under the original design is true) falls below 20%, then the trial will be considered for stopping.

An interim monitoring tool, the most current version of PASS software will be used to estimate the conditional power.

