8.9.1 Analysis of Primary Endpoints

The primary goal of this study is to evaluate the efficacy of the SPT to improve skinfold conditions, including erythema, maceration, denudation, satellite lesions, pain, itching, burning and odor over five days of treatment. Erythema, maceration, denudation, satellite lesions, and odor will be assessed using Likert scales, with "0" being least severe and "4" being most severe. Ordinal mixed models, or other appropriate methods depending on the distribution of data, will be employed to compare the assessment of skin fold

conditions of target areas across five days of treatment, with participants as a random variable and treatment days (Day 0, and Days 1, 3, and 5) as a covariate. Significant omnibus test will be followed by Tukey's post-hoc pairwise comparisons of Day 0 vs Day 1, Day 0 vs Day 3, Day 0 vs Day 5, Day 1 vs Day 3, and Day 3 vs Day 5.

ANOVA/Mixed models, or other appropriate methods depending on the distribution of data, will be conducted to compare VAS scores of discomfort (pain, itching, or burning) reported by participants on Day 0, and Days 1, 3, and 5. Significant omnibus test will be followed by Tukey's post-hoc pairwise comparisons of Day 0 vs Day 1, Day 0 vs Day 3, Day 0 vs Day 5, Day 1 vs Day 3, and Day 3 vs Day 5. In addition, descriptive statistics for the most prominent discomfort in the target area will also be reported in this study.

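### Photographs reach the scorer in the order taken, so the only rater of four primary signs can tell Day 0 from later images

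*Combined protocol and SAP*

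**What the plan says.** - **Order of reading.** Section 6.4 has the photographs from Days 0, 1, 3 and 5 (or the last day) scored after dismissal. They "will be bundled and provided (in the order in which the photographs are taken) to the third-party clinician".
- **Who scores.** Section 1.1 describes the rater as "An independent licensed clinician with experience in identifying and treating skin fold conditions". Sections 1.1, 3, 4.1, 6.4 and 8.6.1 all give this one person the scoring of erythema, maceration, denudation and satellite lesions, which form primary endpoint component 1a. Under section 6.1.2 the investigator's team also records these signs, but only at screening.
- **Masking and control.** Section 4.1 states: "This is a prospective unblinded study". Section 8.2 states: "No randomization is planned at this time". No control arm is described.
- **Analysis.** Section 8.9.1 fits ordinal mixed models with treatment day as covariate. A significant omnibus test leads to Tukey "post-hoc pairwise comparisons of Day 0 vs Day 1, Day 0 vs Day 3, Day 0 vs Day 5", and also Day 1 vs 3 and Day 3 vs 5.
- **Early end.** Under section 6.3, if the skin fold conditions "resolve before Day 5, the last day of study participation will occur on that day".
- **Interim looks.** Section 8.5 sets them after about 40 and 80 target "areas have been assessed and adjudicated". It defines no adjudication procedure.

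**The concern.** In a single-arm study, visit day plays the part that treatment allocation plays in a randomized one: it is the contrast being tested. A rater who receives the images in time order knows which is baseline and which were taken under treatment, even if every date is removed. A tendency to score later images as better, or to look for a smooth improvement, passes straight into the Day 0 contrasts for four primary signs.

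A larger sample does not remove such a shift, and no term in the section 8.9.1 model can isolate it. Once scoring is done, only a masked re-read of the stored photographs could measure it.

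The loss is avoidable. Treatment cannot be hidden in a one-arm study, but the day can be hidden from someone who scores photographs after the participant has left. A bundle that stops before Day 5 may also tell the rater that the site judged the area resolved.

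**Working it through.** **Step 1. Can the rater identify Day 0?** Yes. Section 6.4 fixes the order, so the first image is Day 0. No section describes removal of day labels, random order or a second reader. The independence stated in section 1.1, the unblinded label in section 4.1 and the undefined adjudication in section 8.5 do not change this.

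**Step 2. Does the order coincide with the tested factor?** Yes. Section 8.9.1 compares days within target areas, and there is no other comparison group.

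**Step 3. What could a small drift do?** The documents give neither an SD for these Likert scores nor any drift size, so this step is an illustration on assumed values.

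*Inputs from the plan*
- n = 119 target areas (section 8.1). This was sized on VAS pain. It reproduces from a difference of 10, SD 30, two-sided alpha .0083 and 80% power: the paired t-test needs 113, and 113 × π/3 = 118.3, rounded up to 119. Here it serves only as the number of pairs.
- Four assessment days and a 0–4 scale (section 8.9.1).

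*Assumptions*
- No true change.
- Independent pairs.
- SD of the paired change 1.0, varied from 0.75 to 1.25.
- Mean drift b over all 119 areas.

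*Tukey per-pair level.* Error df = (119 − 1) × (4 − 1) = 354. The studentized range quantile for four means is q(.95) = 3.650. Then t = 3.650/√2 = 2.581, a two-sided per-pair level of .0102.

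*Chance of a significant pair.* This is the probability that a noncentral t variable with 118 df and noncentrality (b/SD) × √119 falls beyond the critical value. For b = 0.20 and SD 1.0 the noncentrality is 0.20 × 10.909 = 2.18.

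| Mean drift (points) | Tukey level, .0102 | Unadjusted .05 | .0083 |
|---|---|---|---|
| 0.10 | 6.8% | 19.1% | 5.9% |
| 0.20 | 33.9% | 58.1% | 31.2% |
| 0.25 | 54.8% | 77.2% | 51.9% |
| 0.30 | 74.5% | 90.1% | 72.1% |

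The .0083 column uses the alpha of section 8.1, which was set for VAS pain; sections 8.9 and 8.9.1 govern the Likert signs. For a drift of 0.20 at the Tukey level, SD 1.25 gives 19.9% and SD 0.75 gives 61.8%.

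*Check by simulation.* 8,000 runs used a repeated-measures ANOVA omnibus test at .05 followed by Tukey, with continuous scores standing in for the ordinal model and equal drift on Days 1, 3 and 5. Day 0 vs Day 5 was significant in 6.0%, 33.1%, 55.3% and 75.2% of runs for the four drifts, and in 0.9% with no drift.

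**Step 4. How far does sign prevalence matter?** Section 5.1 admits an area with any one of nine conditions, so an area may score 0 on a given photographed sign and cannot drift lower. Suppose half the areas show the sign (an assumption) and the drift acts only on them. With n = 59 in the same formula, a 0.20 drift gives about 14% and a 0.30 drift about 37% at the Tukey level. With a quarter (n = 30), the figures are about 6% and 16%.

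**The case against.** The strongest reply is that this is an open choice in a declared unblinded, post-market study, not an error. The rater is independent and scores after dismissal. Reading in sequence helps a rater allow for differences in lighting and position, whereas random reading may add noise of unknown size. Masking would also not rescue the attribution: natural course and regression to the mean remain, and odor, pain, itching and burning stay unmasked.

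Much of this stands as context. It limits what the change can achieve, and independence bears on how likely bias is. It does not hide which image is baseline, and the plan gives no reason for ordered reading. Added noise mainly costs precision, whereas expectation can move the mean.

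Two narrower objections also have force. The scale floor and sign prevalence mean that a drift averaged over all 119 areas may overstate the risk for an uncommon sign, as Step 4 shows. And a short bundle signals resolution only if photographs from participants who leave for other reasons (section 5.4) are not sent for scoring, which the plan does not say. Neither affects the main point.

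**Conclusion.** The concern holds. The scorer of four primary signs can see the factor that the primary analysis tests, in a design with no other comparison, and the plan gives up masking that its photographic method would allow. This should be fixed; it does not show that bias has occurred or that the study is invalid.

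The reading of the text needs no assumption. The size does: neither the amount nor the direction of bias can be derived from the documents, and the percentages depend on the assumed drift, SD and sign prevalence. They also assume independent pairs. Section 1.1 says "Participants can be the source of up to two target areas" and permits re-enrolment, so the pairs may be correlated and the figures would then differ.

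**What to change.** Replace the ordering rule in section 6.4 with wording such as:

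> All photographs of one target area on one day form one set. Each set is stripped of date, day and participant labels, given a random code, and presented in random order across days and participants, within batches that match the interim looks (about 40, 80 and 119 target areas). All days of one target area fall in the same batch. The clinician scores each set without access to that area's other days. The codes for a batch are broken only after that batch's scores are locked.

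The assessment days and the last-day rule stay as they are. Because the sets are no longer bundled by participant, an early end is no longer visible to the rater.

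The cost is one revised paragraph, a coded file list and a score lock for each of three batches. The clinician, the photographs and the number of scores per sign, area and day do not change. The downside is that scores may be somewhat noisier than with side-by-side reading.

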7.1. Definition of ADE

An ADE is the adverse event related to the use of an investigational medical device resulting from insufficiencies or inadequacies in the IFU, the deployment, the installation, the operation, or any malfunction of the investigational medical device, or from error in use.

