1.2 Schedule of Activities (SOA)

Assessments and activities [#]	Day 0	Day 1	Day 2	Day 3	Day 4	Day 5/ last day of participation [‡]	Photographic evaluation using the wound camera system
PI or qualified designee obtains informed consent	X						
PI or qualified designee carries out participant screening	X						
As part of screening, PI or qualified designee examines and documents the skin fold conditions to identify potential target area(s)	X						
PI or qualified designee collects applicable demographics and co-morbidities information	X						
PI or qualified designee collects applicable medication information	X	X	X	X	X	X	
PI or qualified designee takes photographs of target areas using the wound camera system	X	X		X		X	
PI or qualified designee assesses skin fold conditions (moisture and odor) in the target area(s)	X	X		X		X	
Participant completes a survey regarding discomfort (pain, itching, and burning) in the target area(s)	X	X		X		X	
Participant identifies the prominent type of discomfort	X	X		X		X	
HCP applies SPT to the target area(s)	X	X	X [§]	X	X [§]		

Assessments and activities [#]	Day 0	Day 1	Day 2	Day 3	Day 4	Day 5/ last day of participation [‡]	Photographic evaluation using the wound camera system
HCP completes a feedback survey regarding their experience with the SPT						X	
Participant completes a survey regarding experience with the SPT						X	
Third-party clinician assesses skin fold conditions such as erythema, maceration, denudation, and satellite lesions							X
Monitoring for adverse events	X	X	X	X	X	X	
Participant dismissal from study activities						X	

[#] Study activities will occur after informed consent has been signed, and the participant has met all the inclusion criteria and none of the exclusion criteria.

[‡] SPT will be changed if clinically warranted.

^{*}If the target area(s) heal before Day 5, all activities planned for Day 5 will be carried out on the last day of study participation.

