7.2. Definition of Serious Adverse Device Event (SADE)

The SADE is the adverse device effect that has resulted in any of the consequences characteristic of a serious adverse event (SAE).

The FDA definition of a SAE will be used in this study: An AE or suspected adverse reaction is considered "serious" if, in the view of either the PI or sponsor, it results in any of the following outcomes:

- Death,
- A life-threatening adverse event,
- Inpatient hospitalization or prolongation of existing hospitalization,
- A persistent or significant incapacity or substantial disruption of the ability to conduct normal life functions, or
- A congenital anomaly/birth defect.

Important medical events that may not result in death, be life-threatening, or require hospitalization may be considered serious when, based upon appropriate medical judgment, they may jeopardize the participant and may require medical or surgical intervention to prevent one of the outcomes listed in this definition. All SADEs will be reported to Medline, regardless of potential relationship to the study product(s). SADEs will be reported to the reviewing IRB as necessary according to their reporting requirements.

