7.5. Relatedness of ADE and SADE

- **Unrelated:** This category applies to those ADEs, which after careful consideration, are clearly and incontrovertibly due to extraneous causes (disease, environment, etc.)
- **Possible:** This category applies to those ADEs for which, after careful medical consideration at the time they are evaluated, a connection with the Investigational Product administration appears unlikely but cannot be ruled out with certainty.
- **Probable:** This category applies to those ADEs, which after careful medical consideration at the time they are evaluated, are felt with a high degree of certainty to be related to the study product(s).
- **Definite:** This category applies to those ADEs, which after careful consideration, are clearly and incontrovertibly due to the study product(s).

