7.7. ADE Reporting

The ADEs will be recorded on the ADE form (provided by Medline) by the qualified designee and reviewed by the PI. Changes in the severity of an ADE will be documented to allow an assessment of the duration of the event at each level of severity. Changes in severity will necessitate a new CRF to document the new level of severity. ADEs characterized as intermittent will require documentation of onset and duration of each episode.

Non-serious ADEs will be reported to the study sponsor on a monthly basis for review or as agreed upon with the study sponsor, and reported to the IRB per IRB reporting requirements.

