8.3. Populations for Analyses

The analyses will be performed on the intent-to-treat population, which consists of all participants who were qualified for entry criteria and adhered to the protocol, meaning completing five days of treatment with complete data on assessment of skin fold conditions, as well as responses on discomfort and overall experience with the SPT.

No per protocol, safety, or other analysis groups are planned.

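### Sections 7.1 and 7.7 tie the recording of adverse events to device-relatedness, in conflict with 1.2, 7.2, 7.5 and 9.2.3, and no safety summary is planned

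*Combined protocol and SAP*

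**What the plan says.** The safety text of the combined protocol and SAP uses two vocabularies.

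**Device-event vocabulary**
- Section 7.1: "An ADE is the adverse event related to the use of an investigational medical device", where the event results from shortcomings in the IFU, or from deployment, installation, operation, malfunction or use error.
- Section 7.7: "The ADEs will be recorded on the ADE form". This is the only recording rule for non-serious events.
- Section 7.2 defines a SADE as a serious form of adverse device effect. Section 7.3 requires a UADE to be caused by or associated with the device.
- Section 9.2.2 limits safety oversight by the PI to visit activity, ADEs and SADEs.

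**General adverse-event vocabulary**
- Section 1.2 schedules "Monitoring for adverse events" on every day from Day 0 to Day 5, with no restriction to device-related events.
- Section 5.4 allows participation to end because of adverse events, not ADEs.
- Section 7.5 grades relatedness and includes an Unrelated class for ADEs that "are clearly and incontrovertibly due to extraneous causes".
- Section 7.2 requires SADEs to be reported to the sponsor "regardless of potential relationship to the study product(s".
- Section 9.2.3 lists unacceptable risk found on AE review as a ground for suspending or terminating the study.

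On analysis, section 8.3 defines one set, made up of participants who adhered to the protocol and have complete data, and adds: "No per protocol, safety, or other analysis groups are planned". Section 8.9 specifies no safety summary.

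**The concern.** If relatedness is part of the definition of the thing recorded, someone must judge causality before the form is opened. Here that would be unblinded site staff, in a study with no randomised comparator. The judgement is not easy. Section 2.1 itself says that worsening erythema or satellite lesions may point to secondary infection, so putting deterioration under the textile down to the disease would often be reasonable, and there is no control rate to check it against.

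At stake are three things: whether sites record the same kinds of event, whether the review that 9.2.3 relies on has the data it needs, and whether the study can describe harms in everyone exposed to the product.

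**Working it through.** No arithmetic applies. The check is to set the sections side by side and follow particular events through them.

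**Step 1: is the definition compatible with the scale?** Under 7.1 an ADE is already related to device use. Section 7.5 then sorts ADEs into Unrelated, Possible, Probable and Definite. Under 7.1 the Unrelated class is empty by definition, and Possible, which 7.5 describes as a connection that appears unlikely, fits poorly. The same clash sits inside 7.2: a SADE is a device effect, yet it is reported whatever its relationship to the product.

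**Step 2: follow three events.**
- *Non-serious worsening of a target area that the site attributes to the disease.* By 7.1 it is not an ADE, so 7.7 does not call for the form. By 7.5 it is an ADE classed as Unrelated and does go on the form. The sentence in 7.2 does not settle it, because it covers serious events only.
- *Allergic reaction to the fabric, hydrogen peroxide or tape, with the SPT used as instructed.* Section 2.3.1 names this as the potential risk to participants. It is related to use, but 7.1 also asks that the event result from one of the listed instruction, device or use causes. A reaction to a product that works and is applied as intended does not clearly meet that condition. The UADE route in 7.3 does not fill the gap: it covers serious problems, and allergy is already identified in the plan.
- *Serious event that the site considers unrelated.* By the definition in 7.2 it is not a SADE; by the reporting sentence in 7.2 it is to be reported.

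In the first and third cases two sites could each follow the text and act differently.

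**Step 3: is there another recording route?** Sections 7.1 to 7.8 give a form for ADEs (7.7) and a form for SADEs (7.8). The document states no form, log or rule for an adverse event judged not device-related. The general terms in 1.2, 5.4 and 9.2.3 therefore have no matching recording rule.

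**Step 4: what reaches the analysis?** Under 5.4 a participant who leaves because of adverse events is replaced until the study has 119 target areas. Under 8.3 the analysis set requires five days of treatment with complete data; 5.4 counts early healing, but not early withdrawal for harm, as complete. There is no safety group, and 8.9 contains no safety table. Events in participants who leave for harm thus enter no planned summary, even where they were recorded as ADEs.

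**The case against.** The strongest reply is that ADE is used loosely for any event. Section 7.5 grades relatedness when the event is evaluated and provides for unrelated events; 7.7 has the designee record and the PI then review; no section tells staff to decide causality before writing anything down. That reading is plausible, and a site may follow it. It stands as a reason not to assert that events are in fact being filtered. It does not remove the conflict with 7.1, and it leaves capture dependent on which section a site follows.

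A second reply is that worsening skin is what the study measures. This is partly right. Photographs, odor and moisture ratings and discomfort VAS scores are taken on Days 0, 1, 3 and 5; medication information is collected daily; additional care goes in the CRF (6.2.2.1); extra SPT changes are logged with reasons (8.7). A reader might infer that an event attributed to disease leaves no trace at all; the documents do not support that. What these traces lack is the severity, seriousness and relatedness grading of section 7, and the analysis set excludes participants without complete data.

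Third, the sponsor has source data review (9.1) and access to medical records (9.2.1), so it would be too strong to say that it could never find an unrecorded event. Those are monitoring safeguards, not a recording rule.

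Finally, for a marketed textile used for up to six days, device-focused recording is a defensible scope. That is fair, but the scope should then be stated consistently and should clearly cover the risk named in 2.3.1.

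**Conclusion.** The inconsistency is established on the text: 7.1 and 7.7 do not fit 1.2, 7.2, 7.5 or 9.2.3. So is the gap in analysis: a completers-only set, replacement of participants who leave for adverse events, and no safety summary. Filtering by attribution before recording is what 7.1 means if read literally; it is not shown to be what sites do. The conclusion rests on the protocol wording alone. The CRFs and the ADE form are supplied separately and could contain fields that narrow the gap.

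The size of any under-recording cannot be computed. A reader might want to say that a count of zero events would carry a misleading upper confidence bound. The documents do not support putting a figure on that: safety is neither an objective nor an endpoint in section 3, no event-rate inference is planned, and the denominator is unknown. Replacement can raise the number treated, while two target areas per participant and re-enrolment under new IDs lower the number of distinct persons. Nor does the risk statement in 2.3.3 rest on this study's event count; it is made in advance, from marketed status and minimal risk.

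The efficacy analysis and the sample size are not affected. The point should be corrected because it bears on completeness of harms data and the remedy is cheap.

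**What to change.** - Reconcile 1.2, 5.4, 7.1, 7.2, 7.5, 7.7, 9.2.2 and 9.2.3 so that one term covers the events that are monitored, recorded, overseen and reviewed. For 5.4 and 9.2.3 this concerns the term used, not the decision rules.
- State that adverse events from first SPT application to last study day are recorded first, on the existing form, and only then classified with the 7.5 scale. At minimum this should cover all serious events, all target-area events, and any suspected reaction to the SPT or the tape wherever it occurs. A rule confined to the target area would miss an allergic reaction elsewhere on the body.
- In 8.3, add a descriptive safety table in all participants with at least one SPT application, including those withdrawn or replaced, by severity, seriousness and relatedness. Because of re-enrolment, say whether the denominator is persons or study IDs.

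Cost: revised wording, some additional forms for events later classed as unrelated (limited by participation of up to six days), and one table. Sample size, visits and treatment do not change.
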